5.2.2 Timing of Dose Administration

Trial treatment should be administered on Day 1 of each cycle after all procedures/assessments have been completed as detailed on the Study Calendar ([Section 6.0](#)). Trial treatment may be administered up to 3 days before or after the scheduled Day 1 of each cycle due to administrative reasons.

All pembrolizumab treatment will be administered on an outpatient basis. Palliative radiotherapy is permitted to be delivered as an inpatient if in line with patient standard-of-care and after discussion with the study PI.

Pembrolizumab 200 mg will be administered as a 30 minute IV infusion every 3 weeks. Sites should make every effort to target infusion timing to be as close to 30 minutes as possible. However, given the variability of infusion pumps from site to site, a window of -5 minutes and +10 minutes is permitted (i.e., infusion time is 30 minutes: -5 min/+10 min).

The Pharmacy Manual contains specific instructions for the preparation of the pembrolizumab infusion fluid and administration of infusion solution.

5.2.3 External Beam Radiotherapy

5.2.3.1 General Radiotherapy Information

The intent of treatment is to deliver a palliative course of radiotherapy to a total dose of 30 Gy in 10 fractions to the symptomatic primary disease sites in the esophageal, GE junction, or gastric areas or one of the metastases. Both 3D conformal radiotherapy and IMRT are allowed.

Megavoltage equipment with effective photon energies \geq 6MV is required.

Technique: 3D conformal using opposed AP-PA portals or multifield techniques, such as AP, PA and opposed lateral fields or IMRT are recommended. ICRU-50 and ICRU-62 prescription methods and nomenclature shall be used in this trial. Tightly contoured targets should be used to spare as much bone marrow, small bowel, liver, heart, lung and kidney as possible.

The prescription volume is the planning target volume (PTV). The total dose is 30 Gy in 10 fractions. A minimum of 90% of the PTV will receive 30 Gy. No more than 10% of the PTV shall receive greater than 35 Gy.

5.2.3.2 Localization, Simulation, and Immobilization

Prior to the simulation, all pertinent radiographs, operative notes, and other diagnostic procedures such as endoscopic findings should be reviewed. This will allow an informed determination of target volume and treatment field borders.

Simulation is required for all patients and should be performed with the patient positioned in an individualized immobilization device in the treatment position on a flat hard table and it is better in the supine position. Simulation must be performed on a diagnostic quality radiation

IRB Protocol No. 16099

Version Date: 10/16/2019

Version: 04

therapy simulator, which reproduces the geometry of the treatment machine. Oral contrast can be used to help outlining the target volume in the esophageal/GE junction/gastric areas. CT-based treatment planning is required for this study. The planning CT should encompass the entire thoracic cavity for esophageal/GE junction cancer and the abdominal to a level below the bottom of the kidneys for gastric cancer. A maximum slice thickness of 3-5 mm is required through regions of the gross tumor volume (GTV).

5.2.3.3 Treatment Planning and Target Volumes

Gross Target Volume (GTV): The GTV is defined as the primary tumor in the esophageal/GE junction/gastric areas, the grossly enlarged lymph nodes, or the gross metastatic sites requiring a palliative course of radiotherapy.

Clinical Target Volume (CTV): Since the intent of radiotherapy is for palliation, there is no need to define a CTV for treatment.

Planning Target Volume (PTV): Margins shall be added to the GTV for set up error and movement as PTV. This expansion could be 0.5 to 2 cm and does not need to be uniform in all dimensions. 4DCT scan is allowed to customize PTV expansion.

3D conformal radiotherapy or IMRT should be planned to optimize the PTV coverage and a minimum of 90% of the PTV shall receive 30 Gy. No more than 10% of the PTV shall receive greater than 35 Gy. IMRT can be delivered by tomotherapy or TrueBeam using RapidArc technique.

5.2.3.4 Critical Structures and Compliance Criteria

Organs at risk including lungs, liver, heart, kidneys and spinal cord shall be contoured. Dose constraints must follow the standard guidelines. The treating physician must carefully consider the tolerance dose/volume to each critical normal structure. It is recommended to reduce doses to lung and heart as much as possible.

- Lung: mean dose \leq 20 Gy, V30 \leq 20%, V20 \leq 25%, V10 \leq 40% and V5 \leq 50%
- Heart: mean dose \leq 25 Gy, V30 \leq 30%
- Kidney: V20 \leq 30%
- Liver: mean dose \leq 20 Gy, V30 \leq 30%

5.2.3.5 Radiotherapy Adverse Events

Adverse effects related to radiation therapy will be recorded. These include nausea/vomiting, diarrhea, poor appetite, weight loss, fatigue, skin erythema, esophagitis, carditis, pneumonitis, myelosuppression, myelitis, late pulmonary fibrosis, and esophageal stricture.

5.3 Concomitant Medications/Vaccinations (allowed & prohibited)

Medications or vaccinations specifically prohibited in the exclusion criteria are not allowed during the ongoing trial. If there is a clinical indication for one of these or other medications or vaccinations specifically prohibited during the trial, discontinuation from trial therapy or vaccination may be required. The investigator should discuss any questions regarding this with the Merck Clinical team. The final decision on any supportive therapy or vaccination rests with the investigator and/or the subject's primary physician.

5.3.1 Acceptable Concomitant Medications

All treatments that the investigator considers necessary for a subject's welfare may be administered at the discretion of the investigator in keeping with the community standards of medical care. All concomitant medication will be recorded on the case report form (CRF) including all prescription, over-the-counter (OTC), herbal supplements, and IV medications and fluids. If changes occur during the trial period, documentation of drug dosage, frequency, route, and date may also be included on the CRF.

All concomitant medications received within 28 days before the first dose of trial treatment and 30 days after the last dose of trial treatment should be recorded. Concomitant medications administered after 30 days after the last dose of trial treatment should be recorded for SAEs and ECIs as defined in [Section 8.0](#).

5.3.2 Prohibited Concomitant Medications

Subjects are prohibited from receiving the following therapies during the Screening and Treatment Phase (including retreatment for post-complete response relapse) of this trial:

- Antineoplastic systemic chemotherapy or biological therapy
- Immunotherapy not specified in this protocol
- Chemotherapy not specified in this protocol
- Investigational agents other than pembrolizumab
- Radiation therapy outside of the clinical target volume of the index target lesion
 - Note: Radiation therapy to a symptomatic lesion other than the index target lesion or to the brain may be allowed at the investigator's discretion if the radiation course occurs after radiation has completed to the index target lesion.
- Live vaccines within 30 days prior to the first dose of trial treatment and while participating in the trial. Examples of live vaccines include, but are not limited to, the following: measles, mumps, rubella, varicella/zoster, yellow fever, rabies, BCG, and typhoid vaccine.

- Systemic glucocorticoids for any purpose other than to modulate symptoms from an event of clinical interest of suspected immunologic etiology. The use of physiologic doses of corticosteroids may be approved after consultation with the Sponsor.

Subjects who, in the assessment by the investigator, require the use of any of the aforementioned treatments for clinical management should be removed from the trial. Subjects may receive other medications that the investigator deems to be medically necessary.

The Exclusion Criteria describes other medications which are prohibited in this trial.

There are no prohibited therapies during the Post-Treatment Follow-up Phase.

5.4 Rescue Medications & Supportive Care

5.4.1 Supportive Care Guidelines

Subjects should receive appropriate supportive care measures as deemed necessary by the treating investigator. Suggested supportive care measures for the management of adverse events with potential immunologic etiology are outlined below and in greater detail in the ECI guidance document. Where appropriate, these guidelines include the use of oral or intravenous treatment with corticosteroids as well as additional anti-inflammatory agents if symptoms do not improve with administration of corticosteroids. Note that several courses of steroid tapering may be necessary as symptoms may worsen when the steroid dose is decreased. For each disorder, attempts should be made to rule out other causes such as metastatic disease or bacterial or viral infection, which might require additional supportive care. The treatment guidelines are intended to be applied when the investigator determines the events to be related to pembrolizumab.

Note: if after the evaluation the event is determined not to be related, the investigator is instructed to follow the ECI reporting guidance but does not need to follow the treatment guidance (as outlined in the ECI guidance document). Refer to [Section 5.2.1](#) for dose modification.

It may be necessary to perform conditional procedures such as bronchoscopy, endoscopy, or skin photography as part of evaluation of the event. Suggested conditional procedures, as appropriate, can be found in the ECI guidance document.

- **Pneumonitis:**
 - For **Grade 2 events**, treat with systemic corticosteroids. When symptoms improve to Grade 1 or less, steroid taper should be started and continued over no less than 4 weeks.
 - For **Grade 3-4 events**, immediately treat with intravenous steroids. Administer additional anti-inflammatory measures, as needed.
 - Add prophylactic antibiotics for opportunistic infections in the case of prolonged steroid administration.

- **Diarrhea/Colitis:**

Subjects should be carefully monitored for signs and symptoms of enterocolitis (such as diarrhea, abdominal pain, blood or mucus in stool, with or without fever) and of bowel perforation (such as peritoneal signs and ileus).

- All subjects who experience diarrhea/colitis should be advised to drink liberal quantities of clear fluids. If sufficient oral fluid intake is not feasible, fluid and electrolytes should be substituted via IV infusion. For Grade 2 or higher diarrhea, consider GI consultation and endoscopy to confirm or rule out colitis.
- For **Grade 2 diarrhea/colitis** that persists greater than 3 days, administer oral corticosteroids.
- For **Grade 3 or 4 diarrhea/colitis** that persists > 1 week, treat with intravenous steroids followed by high dose oral steroids.
- When symptoms improve to Grade 1 or less, steroid taper should be started and continued over no less than 4 weeks.

- **Type 1 diabetes mellitus (if new onset, including diabetic ketoacidosis [DKA]) or \geq Grade 3 Hyperglycemia, if associated with ketosis (ketonuria) or metabolic acidosis (DKA)**

- For **T1DM or Grade 3-4 Hyperglycemia**
 - Insulin replacement therapy is recommended for Type I diabetes mellitus and for Grade 3-4 hyperglycemia associated with metabolic acidosis or ketonuria.
 - Evaluate patients with serum glucose and a metabolic panel, urine ketones, glycosylated hemoglobin, and C-peptide.

- **Hypophysitis:**

- For **Grade 2** events, treat with corticosteroids. When symptoms improve to Grade 1 or less, steroid taper should be started and continued over no less than 4 weeks. Replacement of appropriate hormones may be required as the steroid dose is tapered.
- For **Grade 3-4** events, treat with an initial dose of IV corticosteroids followed by oral corticosteroids. When symptoms improve to Grade 1 or less, steroid taper should be started and continued over no less than 4 weeks. Replacement of appropriate hormones may be required as the steroid dose is tapered.

- **Hyperthyroidism or Hypothyroidism:**

Thyroid disorders can occur at any time during treatment. Monitor patients for changes in thyroid function (at the start of treatment, periodically during treatment, and as indicated based on clinical evaluation) and for clinical signs and symptoms of thyroid disorders.

- **Grade 2** hyperthyroidism events (and **Grade 2-4** hypothyroidism):

- In hyperthyroidism, non-selective beta-blockers (e.g. propranolol) are suggested as initial therapy.
- In hypothyroidism, thyroid hormone replacement therapy, with levothyroxine or liothyroinine, is indicated per standard of care.
- **Grade 3-4 hyperthyroidism**
 - Treat with an initial dose of IV corticosteroid followed by oral corticosteroids. When symptoms improve to Grade 1 or less, steroid taper should be started and continued over no less than 4 weeks. Replacement of appropriate hormones may be required as the steroid dose is tapered.
- **Hepatic:**
 - For **Grade 2** events, monitor liver function tests more frequently until returned to baseline values (consider weekly).
 - Treat with IV or oral corticosteroids
 - For **Grade 3-4** events, treat with intravenous corticosteroids for 24 to 48 hours.
 - When symptoms improve to Grade 1 or less, a steroid taper should be started and continued over no less than 4 weeks.
- **Renal Failure or Nephritis:**
 - For **Grade 2** events, treat with corticosteroids.
 - For **Grade 3-4** events, treat with systemic corticosteroids.
 - When symptoms improve to Grade 1 or less, steroid taper should be started and continued over no less than 4 weeks.
- **Management of Infusion Reactions:** Signs and symptoms usually develop during or shortly after drug infusion and generally resolve completely within 24 hours of completion of infusion.

Table 3 below shows treatment guidelines for subjects who experience an infusion reaction associated with administration of pembrolizumab (MK-3475).

Table 3 Infusion Reaction Treatment Guidelines

NCI CTCAE Grade	Treatment	Premedication at subsequent dosing
Grade 1 Mild reaction; infusion interruption not indicated; intervention not indicated	Increase monitoring of vital signs as medically indicated until the subject is deemed medically stable in the opinion of the investigator.	None
Grade 2 Requires infusion interruption but responds promptly to symptomatic treatment (e.g., antihistamines, NSAIDS, narcotics, IV fluids);	Stop Infusion and monitor symptoms. Additional appropriate medical therapy may include but is not limited to: IV fluids Antihistamines NSAIDS	Subject may be premedicated 1.5h (\pm 30 minutes) prior to infusion of pembrolizumab (MK-3475) with:

NCI CTCAE Grade	Treatment	Premedication at subsequent dosing
prophylactic medications indicated for <=24 hrs	
Acetaminophen Narcotics
 
Increase monitoring of vital signs as medically indicated until the subject is deemed medically stable in the opinion of the investigator.
 
If symptoms resolve within one hour of stopping drug infusion, the infusion may be restarted at 50% of the original infusion rate (e.g., from 100 mL/hr to 50 mL/hr). Otherwise dosing will be held until symptoms resolve and the subject should be premedicated for the next scheduled dose.
 
Subjects who develop Grade 2 toxicity despite adequate premedication should be permanently discontinued from further trial treatment administration.
	
Diphenhydramine 50 mg po or IV (or equivalent dose of antihistamine).
 
Acetaminophen 500-1000 mg po (or equivalent dose of antipyretic).

Grades 3 or 4	
Stop Infusion.
 
Additional appropriate medical therapy may include but is not limited to:
 
IV fluids Antihistamines NSAIDS Acetaminophen Narcotics Oxygen Pressors Corticosteroids Epinephrine
 
Increase monitoring of vital signs as medically indicated until the subject is deemed medically stable in the opinion of the investigator.
 
Hospitalization may be indicated.
 
Subject is permanently discontinued from further trial treatment administration.
	No subsequent dosing
Appropriate resuscitation equipment should be available in the room and a physician readily available during the period of drug administration.		

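### Suggested steroid timing for pembrolizumab-related diarrhea/colitis in section 5.4.1 runs opposite to severity: a wait of more than 3 days at Grade 2, but more than 1 week at Grade 3-4

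*Combined protocol and SAP*

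**What the plan says.** Section 5.4.1 lists suggested supportive measures by organ and grade. Under Diarrhea/Colitis, Grade 2 disease "that persists greater than 3 days, administer oral corticosteroids". The next bullet covers Grade 3 or 4 disease "that persists > 1 week, treat with intravenous steroids followed by high dose oral steroids". The same entry asks investigators to watch for enterocolitis and bowel perforation, and to consider GI consultation and endoscopy from Grade 2 upward.

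Elsewhere in the section, Grade 3-4 pneumonitis carries the instruction "immediately treat with intravenous steroids", and for Grade 3-4 hepatic events the text is "treat with intravenous corticosteroids for 24 to 48 hours".

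On scope, the section states: "The treatment guidelines are intended to be applied when the investigator determines the events to be related to pembrolizumab". On status, it describes the measures as suggestions that "are outlined below and in greater detail in the ECI guidance document". Section 5.2.1.2 sends the reader to 5.4.1 and to that guidance document for the use of corticosteroids.

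**The concern.** A treatment threshold for an immune-related toxicity would normally shorten, or disappear, as the grade rises. Here it lengthens. An investigator who followed the two bullets literally would start oral steroids for moderate colitis after 3 days but hold back intravenous steroids for severe or life-threatening colitis until a week had passed. The entry itself names perforation as something to look for, and Table 2 in section 5.2.1.2 stops pembrolizumab permanently at Grade 4, so the protocol plainly regards the event as dangerous. What is at stake is patient safety and the internal consistency of the guidance. No endpoint, analysis or sample-size figure depends on it.

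**Working it through.** The plan gives no figure to reproduce. The check sets the texts side by side.

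**Step 1. The two thresholds (5.4.1, Diarrhea/Colitis).**
- Grade 2: more than 3 days, then oral corticosteroids.
- Grade 3-4: more than 1 week (7 days), then intravenous steroids followed by high-dose oral steroids.
- Difference: 7 - 3 = 4 days, longer for the more severe event.

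**Step 2. Every organ-specific steroid rule in 5.4.1.**

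| Event | Stated wait, Grade 2 | Stated wait, Grade 3-4 |
|---|---|---|
| Pneumonitis | none | none (immediate) |
| Diarrhea/colitis | more than 3 days | more than 7 days |
| Hypophysitis | none | none |
| Hyperthyroidism | no steroid rule (beta-blocker) | none |
| Hepatic | none | none |
| Renal | none | none |

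The 24 to 48 hours in the hepatic Grade 3-4 rule is a length of treatment, not a wait. Type 1 diabetes/hyperglycemia (insulin) and infusion reactions (Table 3, where corticosteroids are only an optional entry) are left out.

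So 1 of 6 Grade 3-4 steroid rules states a wait. Of the 5 events with a steroid rule at both levels, diarrhea/colitis is the only one in which the higher grade waits longer. The hepatic Grade 2 cell assumes that a separate steroid bullet belongs to Grade 2, which the extracted layout suggests but does not prove. The Grade 3-4 comparison does not depend on it.

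**Step 3. Does any other line supply an earlier instruction?**
- The 3-day bullet is limited to Grade 2, so it does not cover an event that begins at Grade 3 or 4.
- Table 2 governs holding and stopping pembrolizumab. It does not say when steroids start.
- Section 5.3.2 permits systemic glucocorticoids "to modulate symptoms from an event of clinical interest of suspected immunologic etiology". That allows early use but does not advise it.

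**Step 4. Could the longer wait be time to exclude other causes?** Section 5.4.1 does ask that metastatic disease and infection be ruled out, and section 5.2.3.5 lists diarrhea as a radiotherapy effect. But the treatment guidelines apply once the investigator has judged the event related to pembrolizumab, and this holds at every grade. Work-up time therefore gives no reason for a longer wait at Grade 3-4 than at Grade 2.

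**The case against.** The best defence has three parts.

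- **The fuller instruction is elsewhere.** The bullets outline a guidance document (Appendix 3) whose text is not reproduced. An investigator using both might never meet this wait. That stands as a limit on what can be said about practice. It does not make the visible wording right, because 5.2.1.2 names 5.4.1 as a place to look for steroid use.
- **The text is advisory.** Supportive care is left to the treating investigator, steroids for a suspected immunologic event are allowed at any time, and GI work-up is to be considered from Grade 2. This stands too, and it rules out any claim about the actual delay.
- **The one-week condition may govern only a step up.** A patient who worsens from Grade 2 may already be on oral steroids, with one week marking the move to intravenous treatment. The documents do not say so, and the reading leaves onset at Grade 3 or 4 without any earlier steroid instruction.

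A reader might infer that the protocol forbids steroids for severe colitis during the first week, or that patients will be treated 4 days late. Neither follows: 5.3.2 sets no waiting period, and the thresholds are advice, not start dates. A reader might also suspect that the drug-hold rules are inverted. They are not. For diarrhea/colitis, Table 2 holds at Grade 2-3 and discontinues at Grade 4.

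**Conclusion.** The inversion is plain on the face of section 5.4.1 and worth correcting. The Grade 3-4 threshold is 4 days longer than the Grade 2 threshold, and it is the only stated wait among the six Grade 3-4 organ steroid rules. Confidence in this reading of the text is high. The clinical effect is unknown: it depends on how investigators use advisory text and on guidance that cannot be seen here. With 14 patients planned, few, if any, would be affected.

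A reader might go on to infer a matching fault in the AST/ALT rules of Table 2, namely that a patient with liver metastases who enters at Grade 2 must improve on the entry value or be discontinued. The documents do not support extending the point that far. Footnote 1 is attached to the Grade 3-4 line, not the Grade 2 line. The Grade 2 discontinuation cell refers only to failure to resolve within 12 weeks and does not define resolution as Grade 0-1, although the restart cell does use that target. The places where the protocol uses baseline as a standard concern liver-test monitoring and recovery from prior therapy at entry.

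**What to change.** Delete the one-week persistence condition from the Grade 3-4 diarrhea/colitis bullet in 5.4.1, so that it reads like the other Grade 3-4 rules in the section. If some wait is wanted, set it no longer than the 3 days used for Grade 2.

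At the same time, check the guidance referred to in Appendix 3 for the same wording. If it carries the same one-week condition, state in the protocol that the earlier treatment applies in this trial, so that investigators do not face two conflicting instructions.

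The cost is one phrase changed by amendment and one check of a document the sponsor already uses. It needs no extra visits, tests or patients, and nothing in the statistical section changes.

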5.5 Diet/Activity/Other Considerations

5.5.1 Diet

Subjects should maintain a normal diet unless modifications are required to manage an AE such as diarrhea, nausea or vomiting.

